5.3 Trial Blinding/Masking

This is an open-label trial; therefore, the Sponsor, investigator, and subject will know the treatment administered.

5.4 Randomization or Treatment Allocation

All patients enrolled in this study will receive the combination of MK-3475 and vorinostat.

5.5 Concomitant Medications/Vaccinations (allowed & prohibited)

Medications or vaccinations specifically prohibited in the exclusion criteria are not allowed during the ongoing trial. If there is a clinical indication for one of these or other medications or vaccinations specifically prohibited during the trial, discontinuation from trial therapy or vaccination may be required. The investigator should discuss any questions regarding this with the Sponsor. The final decision on any supportive therapy or vaccination rests with the investigator and/or the subject's primary physician. However, the decision to continue the subject on trial therapy or vaccination schedule requires the mutual agreement of the Investigator, the Sponsor, and the subject.

Hematopoetic growth factors will not be permitted in patients enrolled on this study.

5.5.1 Acceptable Concomitant Medications

All treatments that the investigator considers necessary for a subject's welfare may be administered at the discretion of the investigator in keeping with the community standards of medical care.

5.5.2 Prohibited Concomitant Medications

Subjects are prohibited from receiving the following therapies during the Screening and Treatment Phase (including retreatment for post-complete response relapse) of this trial:

- Anti-cancer systemic chemotherapy or biological therapy
- Immunotherapy not specified in this protocol
- Chemotherapy not specified in this protocol
- Investigational agents other than MK-3475
- Radiation therapy
 - Note: Radiation therapy to a symptomatic solitary lesion or to the brain may be allowed after consultation with Sponsor.
- Live vaccines within 30 days prior to the first dose of trial treatment and while participating in the trial. Examples of live vaccines include, but are not limited to, the following: measles, mumps, rubella, chicken pox, yellow fever, rabies, BCG, and typhoid (oral) vaccine. Seasonal influenza vaccines for injection are generally killed virus vaccines and are allowed; however intranasal influenza vaccines (e.g. Flu-Mist®) are live attenuated vaccines, and are not allowed..
- Glucocorticoids for any purpose other than to modulate symptoms from an event of clinical interest of suspected immunologic etiology. The use of physiologic doses of corticosteroids may be approved after consultation with the Sponsor.

Subjects who, in the assessment by the investigator, require the use of any of the aforementioned treatments for clinical management should be removed from the trial. Subjects may receive other medications that the investigator deems to be medically necessary.

The Exclusion Criteria describes other medications which are prohibited in this trial.

There are no prohibited therapies during the Post-Treatment Follow-up Phase.

5.6 Rescue Medications & Supportive Care

5.6.1 Supportive Care Guidelines Specific for MK-3475

Subjects should receive appropriate supportive care measures as deemed necessary by the treating investigator including but not limited to the items outlined below:

• Anti-infectives: Subjects with a documented infectious complication should receive oral or IV antibiotics or other anti-infective agents as considered appropriate by the treating investigator for a given infectious condition, according to standard institutional practice.

- Immune-related adverse events: Please see Section 5.6.1.1 below and the separate Pembrolizumab ECI guidance document regarding diagnosis and management of adverse experiences of a potential immunologic etiology.
- Management of Infusion Reactions: Acute infusion reactions (which can include cytokine release syndrome, angioedema, or anaphylaxis) are different from allergic/hypersensitive reactions, although some of the manifestations are common to both AEs. Signs and symptoms usually develop during or shortly after drug infusion and generally resolve completely within 24 hours of completion of infusion. Signs/symptoms may include: Allergic reaction/hypersensitivity (including drug fever); Arthralgia (joint pain); Bronchospasm; Cough; Dizziness; Dyspnea (shortness of breath); Fatigue (asthenia, lethargy, malaise); Headache; Hypertension; Hypotension; Myalgia (muscle pain); Nausea; Pruritis/itching; Rash/desquamation; Rigors/chills; Sweating (diaphoresis); Tachycardia; Tumor pain (onset or exacerbation of tumor pain due to treatment); Urticaria (hives, welts, wheals); Vomiting.

Table 5 below shows treatment guidelines for subjects who experience an infusion reaction associated with administration of MK-3475.

NCI CTCAE Grade	Treatment	Premedication at subsequent dosing
Grade 1 Mild reaction; infusion interruption not indicated; intervention not indicated	Increase monitoring of vital signs as medically indicated until the subject is deemed medically stable in the opinion of the investigator.	None
Grade 2 Requires infusion interruption but responds promptly to symptomatic treatment (e.g., antihistamines, NSAIDS, narcotics, IV fluids); prophylactic medications indicated for < =24 hrs	Stop Infusion and monitor symptoms. Additional appropriate medical therapy may include but is not limited to: IV fluids Antihistamines NSAIDS Acetaminophen Narcotics Increase monitoring of vital signs as medically indicated until the subject is deemed medically stable in the opinion of the investigator. If symptoms resolve within one hour of stopping drug infusion, the infusion may be restarted at 50% of the original infusion rate (e.g. from 100 mL/hr to 50 mL/hr). Otherwise dosing will be held until symptoms resolve and the subject should be premedicated for the next scheduled dose. Subjects who develop Grade 2 toxicity despite adequate premedication should be permanently discontinued from	Subject may be premedicated 1.5h (± 30 minutes) prior to infusion of MK-3475 with: Diphenhydramine 50 mg po (or equivalent dose of antihistamine). Acetaminophen 500-1000 mg po (or equivalent dose of antipyretic).

Table 5 Infusion Reaction Treatment Guidelines

NCI CTCAE Grade	Treatment	Premedication at subsequent dosing
	further trial treatment administration.	
Grades 3 or 4		
Grade 3:	Stop Infusion.	
Prolonged (i.e., not rapidly	Additional appropriate medical therapy may	No subsequent dosing
responsive to symptomatic	include but is not limited to:	
medication and/or brief	IV fluids	
interruption of infusion);	Antihistamines	
recurrence of symptoms following	NSAIDS	
initial improvement;	Acetaminophen	
hospitalization indicated for other	Narcotics	
clinical sequelae (e.g., renal	Oxygen	
impairment, pulmonary infiltrates)	Pressors	
	Corticosteroids	
Grade 4:	Epinephrine	
Life-threatening; pressor or		
ventilatory support indicated	Increase monitoring of vital signs as	
	medically indicated until the subject is	
	deemed medically stable in the opinion of	
	the investigator.	
	Hospitalization may be indicated.	
	Subject is permanently discontinued	
	from further trial treatment	
A	administration.	
	t should be available in the room and a physicia	in readily available during the
period of drug administration.	r to the Common Terminalogy Criteria for Ad-	α
-	r to the Common Terminology Criteria for Adv	erse Evenis v4.0 (CICAE) at
http://ctep.cancer.gov		

5.6.1.1 Supportive Care Guidelines for Events of Clinical Interest and Immune-related Adverse Events (irAEs)

Events of clinical interest of a potential immunologic etiology (irECIs) may be defined as an adverse event of unknown etiology, associated with drug exposure and is consistent with an immune phenomenon. irAEs may be predicted based on the nature of the MK-3475 compound, its mechanism of action, and reported experience with immunotherapies that have a similar mechanism of action. Special attention should be paid to AEs that may be suggestive of potential irAEs. An irAE can occur shortly after the first dose or several months after the last dose of treatment.

If an irAE is suspected, efforts should be made to rule out neoplastic, infectious, metabolic, toxin or other etiologic causes prior to labeling an adverse event as an irAE. Information on how to identify and evaluate irAEs has been developed and is included in the Pembrolizumab Event of Clinical Interest Guidance Document.Subjects who develop a Grade 2 or higher irAE should be discussed immediately with the Sponsor.

Recommendations to managing irAEs not detailed elsewhere in the protocol are detailed in Table 6.

irAE	Withhold/Discontinue MK- 3475?	Supportive Care
Grade 1	No action	Provide symptomatic treatment
Grade 2	May withhold MK-3475	Consider systemic corticosteroids in addition to appropriate symptomatic treatment
Grade 3 and Grade 4	Withhold MK-3475 Discontinue if unable to reduce corticosteroid dose to < 10 mg per day prednisone equivalent within 12 weeks of toxicity	Systemic corticosteroids are indicated in addition to appropriate symptomatic treatment. May utilize 1 to 2 mg/kg prednisone or equivalent per day. Steroid taper should be considered once symptoms improve to Grade 1 or less and tapered over at least 4 weeks.

Table 6 General Approach to Handling irAEs

5.6.1.2 Supportive Care Guidelines for Pneumonitis

Subjects with symptomatic pneumonitis should immediately stop receiving MK-3475 and have an evaluation. The evaluation may include bronchoscopy and pulmonary function tests to rule out other causes such as infection.

If the subject is determined to have study drug associated pneumonitis, the suggested treatment plan is detailed in Table 7.

Table 7 Recommended Approach to Handling Pneumonitis	Table 7	Recommended A	pproach to	Handling Pne	umonitis
--	---------	---------------	------------	--------------	----------

Study drug associated pneumonitis	Withhold/Discontinue MK- 3475?	Supportive Care
Grade 1 (asymptomatic)	No action	Intervention not indicated
Grade 2	Withhold MK-3475, may return to treatment if improves to Grade 1 or resolves within 12 weeks	Systemic corticosteroids are indicated. Taper if necessary.
Grade 3 and Grade 4	Discontinue MK-3475	Systemic corticosteroids are indicated. The use of infliximab may be indicated as appropriate. Refer to the Event of Clinical Interest and Immune-related Adverse Event Guidance Document for additional recommendations.

For Grade 2 pneumonitis that improves to \leq Grade 1 within 12 weeks, the following rules should apply:

- First episode of pneumonitis
 - May increase dosing interval by one week in subsequent cycles
- Second episode of pneumonitis permanently discontinue MK-3475 if upon rechallenge subject develops pneumonitis ≥ Grade 2

5.7 Diet/Activity/Other Considerations

5.7.1 Diet

Subjects should maintain a normal diet unless modifications are required to manage an AE such as diarrhea, nausea or vomiting. Patients on vorinostat are expected to take 2 L of fluid per day.

5.7.2 Contraception

MK-3475 and vorinostat may have adverse effects on a fetus in utero. Furthermore, it is not known if MK-3475 has transient adverse effects on the composition of sperm. Non-pregnant, non-breast-feeding women may be enrolled if they are willing to use 2 methods of birth control or are considered highly unlikely to conceive. Highly unlikely to conceive is defined as 1) surgically sterilized, or 2) postmenopausal (a woman who is \geq 45 years of age and has not had menses for greater than 1 year will be considered postmenopausal), or 3) not heterosexually active for the duration of the study. The two birth control methods can be either two barrier methods or a barrier method plus a hormonal method to prevent pregnancy. Subjects should start using birth control from study Visit 1 throughout the study period up to 120 days after the last dose of study therapy.

Female patients of childbearing potential must have a negative serum pregnancy test (β -hCG) within 72 hours prior to receiving the first dose of vorinostat and should either be postmenopausal, free from menses for > 2 years, surgically sterilized, or willing to use 2 reliable forms of contraception simultaneously, unless abstinence is the chosen method of contraception, starting with visit 1.

Vorinostat may have adverse effects on a fetus in utero. Furthermore, it is not known if vorinostat has transient adverse effects on the composition of sperm. Adequate contraception must be used by all patients (both male and female) and their partners during therapy with vorinostat, and for 30 days after the completion of study drug administration. Women of childbearing potential should be advised to avoid becoming pregnant while receiving treatment with vorinostat.

The following are considered adequate barrier methods of contraception: diaphragm, condom (by the partner), copper intrauterine device, sponge, or spermicide. Appropriate hormonal contraceptives will include any registered and marketed contraceptive agent that contains an estrogen and/or a progestational agent (including oral, subcutaneous, intrauterine, or intramuscular agents).

Subjects should be informed that taking the study medication may involve unknown risks to the fetus (unborn baby) if pregnancy were to occur during the study. In order to participate in the study they must adhere to the contraception requirement (described above) for the duration of the study and during the follow-up period defined in section 7.2.2-Reporting of Pregnancy and Lactation to the Sponsor and to Merck. If there is any question that a subject

will not reliably comply with the requirements for contraception, that subject should not be entered into the study.

5.7.3 Use in Pregnancy

If a subject inadvertently becomes pregnant while on treatment with MK-3475 and/or vorinostat, the subject will immediately be removed from the study. The site will contact the subject at least monthly and document the subject's status until the pregnancy has been completed or terminated. The outcome of the pregnancy will be reported to the Sponsor and to Merck without delay and within 24 hours if the outcome is a serious adverse experience (e.g., death, abortion, congenital anomaly, or other disabling or life-threatening complication to the mother or newborn). The study investigator will make every effort to obtain permission to follow the outcome of the pregnancy and report the condition of the fetus or newborn to the Sponsor. If a male subject impregnates his female partner the study personnel at the site must be informed immediately and the pregnancy reported to the Sponsor and to Merck and followed as described above and in Section 7.2.2.

It is not known if vorinostat may cause fetal harm when administered to a pregnant woman. There are no adequate and well-controlled studies of vorinostat in pregnant women. Results of animal studies indicate that vorinostat crosses the placenta and is found in fetal plasma at levels up to 50% of maternal concentrations. Doses up to 50 and 150 mg/kg/day were tested in rats and rabbits, respectively (~0.5 times the human exposure based on AUC0-24 hours). Treatment-related developmental effects including decreased mean live fetal weights, incomplete ossifications of the skull, thoracic vertebra, sterna, and skeletal variations (cervical ribs, supernumerary ribs, vertebral count and sacral arch variations) in rats at the highest doses of vorinostat tested. Reductions in mean live fetal weight and an elevated incidence of incomplete ossification of the metacarpals were seen in rabbits dosed at 150 mg/kg/day.

The no observed effect levels (NOELs) for these findings were 15 and 50 mg/kg/day (<0.1 times the human exposure based on AUC) in rats and rabbits, respectively. A dose related increase in the incidence of malformations of the gall bladder was noted in all drug treatment groups in rabbits versus the concurrent control. If the drug is used during pregnancy, or if the patient becomes pregnant while taking this drug, the patient should be apprised of the potential hazard to the fetus.

5.7.4 Use in Nursing Women

It is unknown whether MK-3475 is excreted in human milk. Since many drugs are excreted in human milk, and because of the potential for serious adverse reactions in the nursing infant, subjects who are breast-feeding are not eligible for enrollment.

It is not known whether vorinostat is excreted in human milk. Because many drugs are excreted in human milk and because of the potential for serious adverse reactions in nursing infants from vorinostat, a decision should be made whether to discontinue nursing or discontinue the drug, taking into account the importance of the drug to the mother.

5.8 Subject Withdrawal/Discontinuation Criteria

Subjects may withdraw consent at any time for any reason or be dropped from the trial at the discretion of the investigator should any untoward effect occur. In addition, a subject may be withdrawn by the investigator or the Sponsor if enrollment into the trial is inappropriate, the trial plan is violated, or for administrative and/or other safety reasons. Specific details regarding discontinuation or withdrawal are provided in Section 7.1.4 – Other Procedures.

A subject must be discontinued from the trial for any of the following reasons:

- The subject or legal representative (such as a parent or legal guardian) withdraws consent.
- Confirmed radiographic disease progression

Note: For unconfirmed radiographic disease progression, please see Section 5.2.2

Note: A subject may be granted an exception to continue on treatment with confirmed radiographic progression if clinically stable or clinically improved, please see Section 7.2.1.6

- Unacceptable adverse experiences as described in Section 5.2.1.2
- Intercurrent illness that prevents further administration of treatment
- Investigator's decision to withdraw the subject
- The subject has a confirmed positive serum pregnancy test
- Noncompliance with trial treatment or procedure requirements
- The subject is lost to follow-up
- Completed 24 months of treatment with MK-3475

Note: 24 months of study medication is calculated from the date of first dose. Subjects who stop MK-3475 after 24 months may be eligible for up to one year of additional study treatment if they progress after stopping study treatment provided they meet the requirements detailed in Section 5.1.4

• Administrative reasons

The End of Treatment and Follow-up visit procedures are listed in Section 6 (Protocol Flow Chart) and Section 7.1.5 (Visit Requirements). After the end of treatment, each subject will be followed for 30 days for adverse event monitoring (serious adverse events will be collected for 90 days after the end of treatment as described in Section 7.2.3.1). Subjects who discontinue for reasons other than progressive disease will have post-treatment follow-

up for disease status until disease progression, initiating a non-study cancer treatment, withdrawing consent or becoming lost to follow-up.

After documented disease progression each subject will be followed by telephone for overall survival until death, withdrawal of consent, or the end of the study, whichever occurs first.

5.9 Subject Replacement Strategy

Replacement of Patients in DLT Period

Patients who received <90% of the MK-3475 infusion in Cycle 1 (e.g., because the infusion had to be discontinued due to an infusion reaction) and did not experience a DLT will not be taken into account in the assessment of the overall DLT rate for the phase I run in cohort and need to be replaced.

If a patient experiences a DLT in Cycle 1, study therapy may be discontinued following discussion and agreement between the Sponsor and Investigator. An alternative consideration may be dose modifications of Vorinostat and MK-3475 as described in Section 5.2.1.2 with continued therapy.

Specific procedures to be performed during the trial, as well as their prescribed times and associated visit windows, are outlined in the Trial Flow Chart - Section 6.0. Details of each procedure are provided in Section 7.0 - Trial Procedures.

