2.0 TRIAL DESIGN

2.1 Trial Design

This study is an open label, single arm study which will enroll in patients with RMHNSCC and RMSGC. Positive tumor PDL1 expression by IHC will not be required for enrollment.

All patients with receive MK-3475 and vorinostat in combination. Vorinostat will be started on the same day as the initiation of MK-475 200 mg flat dose given Q21 days and continued through the 21 day cycle. Vorinostat will be given 5 out of 7 days at a dose of 400mg QD.

Vorinostat and MK-3475 have well defined toxicities as single agents and have nonoverlapping mechanisms of action. The safety of the two agents used in combination has not been previously described; therefore the study will be conducted in a phase I/II design.

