2.1.1 Phase I run in

Both drugs are FDA approved for other disease indications, with safety and tolerability well described at the approved doses. Therefore the limited phase I portion of this study aims to

assess the safety and tolerability of this drug combination at their established doses. There will be no dose escalation cohorts within this phase I run in group.

The first six patients will constitute the phase I portion of this study. These initial 6 patients may come from either cohort and will be assessed for dose limiting toxicities (DLTs, defined in Section 2.1.1.1) after completion of cycle #1. After these first 6 patients initiate cycle #1, enrollment to the study will be temporarily halted, and a formal DLT evaluation of all 6 patients will be conducted.

If ≤ 2 of these six patients experience DLTs after completion of cycle #1, then the study will proceed to the phase II portion, using MK-3475 200mg IV Q21 days and Vorinostat 400mg PO 5 out of 7 days (x 3 weeks) of each 21 day cycle.

If > 2 of these first 6 patients experience a DLT upon completion of cycle #1, the study will proceed to the phase II portion using MK-3475 IV 200mg Q28 days Vorinostat 300mg daily 5 out of 7 days (x 4 weeks) of each 28 day cycle.

Only upon completion of the DLT evaluation for these first 6 patients and the determination of appropriate Phase II dose, will enrollment reopen for the phase II expansion.

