 Note: Exception to be treated similar to grade 1 toxicity Grade 2 alopecia Grade 2 fatigue For additional information regarding Adverse Events with a potential Immune-Etiology reference Section 5.6.1.1. and Appendix 12.8 	2	Consider withholding for persistent symptoms	Toxicity resolves to Grade 0-1 or baseline	Clinical AE resolves within 4 weeks: Same dose and schedule (reference Section 5.6.1.2 for recommendations regarding pneumonitis) Clinical AE does not resolve within 4 weeks: May increase the dosing interval by 1 week for each occurrence	Toxicity does not resolve within 12 weeks of last infusion
	3, 4	Yes	Toxicity resolves to Grade 0-1 or baseline	May increase the dosing interval by 1 week for each occurrence	Toxicity does not resolve within 12 weeks of last infusion Permanent discontinuation should be considered for any severe or life-threatening event

In case toxicity does not resolve to Grade 0-1 within 12 weeks after last infusion, trial treatment should be discontinued. With investigator and Sponsor agreement, subjects with a laboratory adverse event still at Grade 2 after 12 weeks may continue treatment in the trial only if asymptomatic and controlled. For information on the management of adverse events, see Section 5.6.1.

Subjects who experience a recurrence of the same severe or life-threatening event at the same grade or greater with re-challenge of MK-3475 should be discontinued from trial treatment.

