- A new course of treatment may begin on the scheduled Day 1 of a new cycle if all non-hematological toxicity from the previous cycle has recovered to ≤ Grade 1 or baseline, and/or hematologic recovery documented as outlined in section 5.2.1.4.

Initiation of subsequent cycles of therapy may be delayed for up to 12 weeks to allow recovery from all drug-related toxicity. Alternately, the Investigator may choose to administer supportive care (blood product transfusions) for retreatment criteria to be met. If the recovery criteria are not met after a 12-week delay, the patient will be discontinued from study treatment unless, in the opinion of the Investigator, the patient is experiencing a clinical benefit, in which case a decision regarding continuation of treatment will be made on an individual patient basis in consultation with the Merck medical monitor. Justification will be recorded in the source documents.

When initiating a subsequent cycle, a minimum interval of 21 days should be observed between MK-3475 administrations (with no minimum interval for vorinostat).

Continuation of study therapy during a cycle:

Within any cycle, the dose/schedule of either study drug may be adjusted as necessary.

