7.1.5.3 Post-Treatment Visits

7.1.5.3.1 Safety Follow-Up Visit

The mandatory Safety Follow-Up Visit should be conducted approximately 30 days after the last dose of trial treatment or before the initiation of a new anti-cancer treatment, whichever comes first. All AEs that occur prior to the Safety Follow-Up Visit should be recorded.

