9.6 Returns and Reconciliation

The investigator is responsible for keeping accurate records of the clinical supplies received from Merck or designee, the amount dispensed to and returned by the subjects and the amount remaining at the conclusion of the trial.

Upon completion or termination of the study, all unused and/or partially used investigational product will be destroyed at the site per institutional policy. It is the Investigator's responsibility to arrange for disposal of all empty containers, provided that procedures for proper disposal have been established according to applicable federal, state, local and institutional guidelines and procedures, and provided that appropriate records of disposal are kept.

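### Section 5.9 sets no vorinostat exposure or observation requirement for run-in patients counted as DLT-free, so under-exposed patients could push the 2-of-6 rule towards keeping the starting regimen

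*Combined protocol and SAP*

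**What the plan says.** Section 2.1 gives the reason for the run-in: "The safety of the two agents used in combination has not been previously described". Section 2.1.1 assesses the first six patients for DLTs after completion of Cycle 1, without defining completion. With two or fewer DLTs the starting regimen goes forward; with more than two, "the study will proceed to the phase II portion using MK-3475 IV 200mg Q28 days Vorinostat 300mg daily" applies, on a schedule of 5 days in 7. Section 2.1.2 confirms that this assessment fixes the vorinostat dose and the MK-3475 interval for the expansion.

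Section 5.9 is the only rule on which run-in patients count. Those excluded and replaced are "Patients who received <90% of the MK-3475 infusion in Cycle 1" and who had no DLT. In Cycle 1 that is one Day 1 infusion. Vorinostat is planned for 5 days in 7 over three weeks (Sections 2.1 and 5.2), and no minimum is set for it.

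Three other provisions bear on exposure and follow-up:
- Section 5.2.1.5 allows changes during a cycle: "Within any cycle, the dose/schedule of either study drug may be adjusted as necessary".
- Section 5.8 lists "Noncompliance with trial treatment or procedure requirements" among the reasons for discontinuation, but does not say whether such a patient is evaluable for DLT.
- Section 7.1.5.3.1 places the safety visit "approximately 30 days after the last dose of trial treatment or before the initiation of a new anti-cancer treatment, whichever comes first".

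**The concern.** The protocol already accepts that a DLT-free patient with too little drug says little about toxicity; that is why Section 5.9 replaces patients with an incomplete infusion. It applies the principle to one of the two drugs. The drug left out is the one more open to missed doses, being oral and taken by outpatients over three weeks, in some cases as a suspension through a feeding tube (Sections 5.2.2 and 9.5).

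Safety and tolerability of the combination is the primary objective (Section 3.1), and with six patients each one weighs heavily in the decision. A patient who took little vorinostat and had no DLT enters the count on equal terms with one who took all 15 doses.

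**Working it through.** The plan gives no operating characteristics for the 2-of-6 rule, so there is no stated figure to reproduce.

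**Inputs from the protocol.** Six patients, with the starting regimen kept if at most 2 have a DLT (Section 2.1.1). Planned Cycle 1 vorinostat doses: 5 x 3 = 15, against one MK-3475 infusion.

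**Assumed inputs, because the documents give none.** The true DLT rate under full exposure, p; the chance q that a run-in patient has low vorinostat exposure and still counts; and the DLT risk of such a patient, taken as p/2, with zero as a bound.

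**Step 1. Six fully exposed patients.** P(keep) = P(Bin(6, p) <= 2).

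**Step 2. Exactly one under-exposed patient.** At half risk, P(keep) = (1 - p/2) x P(Bin(5, p) <= 2) + (p/2) x P(Bin(5, p) <= 1). At zero risk, P(keep) = P(Bin(5, p) <= 2). For p = 0.40 the two binomial terms are 0.6826 and 0.3370, so half risk gives 0.8 x 0.6826 + 0.2 x 0.3370 = 0.613.

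| True DLT rate p | Six fully exposed | One at half risk | One at zero risk (bound) |
|---|---|---|---|
| 0.20 | 0.901 | 0.922 | 0.942 |
| 0.30 | 0.744 | 0.791 | 0.837 |
| 0.40 | 0.544 | 0.613 | 0.683 |
| 0.50 | 0.344 | 0.422 | 0.500 |

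**Step 3. Allow for the chance that low exposure occurs.** With probability q of low exposure at half risk, each patient's average risk is p(1 - q/2), and P(keep) = P(Bin(6, p(1 - q/2)) <= 2). For p = 0.40 and q = 0.10 the average risk is 0.38 and P(keep) is 0.586.

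| p | q = 0 | q = 0.05 | q = 0.10 | q = 0.20 | Rise, in points |
|---|---|---|---|---|---|
| 0.20 | 0.901 | 0.907 | 0.913 | 0.924 | 0.6 to 2.3 |
| 0.30 | 0.744 | 0.758 | 0.772 | 0.798 | 1.4 to 5.3 |
| 0.40 | 0.544 | 0.565 | 0.586 | 0.627 | 2.1 to 8.3 |

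The chance that at least one of six is affected is 1 - (1 - q)^6 = 0.265, 0.469 and 0.738 for q = 0.05, 0.10 and 0.20.

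**Step 4. Direction.** Whenever an under-exposed patient's risk is below p, P(keep) rises. If that risk equals p, or if q = 0, nothing changes.

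**The case against.** The strongest reply is that vorinostat toxicity is not ignored. The triggers for vorinostat dose modification in Section 5.2.1.3 nearly repeat the DLT list in Section 2.1.1.1: items 1 to 5 match, and item 6 differs mainly by adding gastrointestinal toxicity. Most mandated modifications in Cycle 1 are therefore DLTs already, if judged related. This stands. It confines the gap mainly to under-exposure for reasons other than toxicity and to early dropout.

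A reader might infer more from three places, and the text does not bear it out:
- **Grade 2 toxicity.** The entry "Consider withholding for persistent symptoms" in the Section 5.2.1.2 table might seem to allow vorinostat to be withheld without a DLT. The surrounding columns speak of the last infusion and the dosing interval, which are MK-3475 terms, and the express hold of both drugs is for Grade 3 or 4. Whether the row governs vorinostat is unclear. Some toxicity-driven loss without a DLT does remain possible, through the within-cycle adjustment in Section 5.2.1.5 or a Grade 3 non-hematologic event of three days or less.
- **Dropouts.** One might say that Section 5.9 orders an early dropout to be counted as DLT-free. Because Section 2.1.1 leaves completion of Cycle 1 undefined, this is an ambiguity and not an instruction. The follow-up of about 30 days after the last dose also covers most short observation, though it restores observation time and not the missing vorinostat.
- **A demonstrated bias.** The documents show an omission. They do not show that low exposure will occur or that it lowers DLT risk.

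A further objection concerns the remedy. Replacing every DLT-free patient who falls short on vorinostat would discard those who stopped because of toxicity below the DLT threshold, and they are evidence against tolerability. This also stands, and the fix allows for it.

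**Conclusion.** The omission is certain. Section 5.9 tests one infusion of one drug, in a run-in meant to test two drugs together. Its effect on the regimen decision is conditional: low vorinostat exposure must occur among the six, and it must lower Cycle 1 DLT risk. If both hold, the error goes only towards keeping the starting regimen.

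On the assumed frequencies and half risk, the averaged shift is modest. A single patient who cannot show a DLT moves the probability from 0.544 to 0.683 at a 40% DLT rate, but that is an upper bound for one such patient and not an estimate. This is a cheap improvement of minor to moderate importance, and not a flaw that invalidates the run-in.

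**What to change.** In Section 5.9:

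1. Define a DLT-evaluable patient as one who has a DLT, or who received a sponsor-specified minimum of both study drugs in Cycle 1 and was observed to the end of the DLT window.
2. Replace DLT-free patients who fall short for reasons unrelated to treatment toxicity, such as non-adherence, withdrawal of consent or loss to follow-up.
3. Keep in the assessment those who fell short because of treatment-related toxicity that was not a DLT, and report them separately to the DLT review.

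The minimum is for the sponsor to set. No exposure threshold, dose or stopping rule is proposed here.

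The cost is protocol wording, possibly one or two replaced run-in patients, and a short delay before enrolment reopens. The records needed to apply a vorinostat minimum are already required: Section 9.6 makes the investigator responsible for "keeping accurate records of the clinical supplies received from Merck or designee, the amount dispensed to and returned by the subjects".
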